7 SCHEDULE OF EVENTS

Table 1: Schedule of Events -- Note: Flexibility in the visit scheduling is allowed (± 3 days) for V2 through V13 – The table shows week numbers approximately

	SAOL Phase ^h									RW Phase					
	Prior to V1 V0 Screening Visit	W 0 V1/ Day0 Baseline	W1 V2/ Day7 SOC Taper	W2 V3/ Day14 SOC Taper	W3 V4/ Day21 SOC Taper	W4 V5/ Day28 SOC Taper	W 8 V6/ Day 56	W 12 V7/ Day 84	W18 V8/ Day 126	W20 V9/ Day 140	W22 V10/ Day 154	W26 V11/ Day 182	W30 V12/ Day 210	W34 V13/ Day 238 Study completion	
Review and signing of Child Assent and Informed Consent Form (ICF)	X														
Demographics and medical history (previous treatments and comorbidities)	X														
Ophthalmic examination		X													
Inclusion/exclusion criteria review	X	X ^a													
Physical exam with specific assessment of hepatosplenomegaly and vital signs	X ^k	X	X	X	X	X	X	X	X	X	X	X	X	X	X
Randomization to Tadeking alfa or placebo (applicable for the RW phase only)		N/A								X					
Standard of Care (SOC) Tapering ^f		X	X	X	X	X									
Treatment with Tadeking alfa (SAOL phase only)		X	X	X	X	X	X	X	X						
Treatment with Tadeking alfa or placebo as randomized in the double blind RW phase (s.c. every 2days) ^b										X ^l	X	X	X	X	X
Review of adverse events (AEs, AESIs) & concomitant medications	X	X	X	X	X	X	X	X	X	X	X	X	X	X	X
Local Tolerability Index assessment ^c		X	X	X	X	X	X	X	X	X	X	X	X	X	X
Physician global clinical evaluation: mAIDAI	X	X	X	X	X	X	X	X	X	X	X	X	X	X	X
Physician Global Assessment (PGA)	X	X	X	X	X	X	X	X	X	X	X	X	X	X	X
Patient's/caregiver's evaluation of health status		X								X					X
Genetic evaluation, infection evaluations (CMV, EBV, etc.), and serology (HIV, HCV, HBV),	X														
Hematology, clinical chemistry, ESR (at local lab), urinalysis, CRP and Ferritin, coagulation (platelets, fibrinogen, D-dimer, PTT, PT) -- (sample taken prior to treatment), pregnancy test ^g ^l TB blood test ^d ^l	X ^l	X	X	X	X	X	X	X	X ^l	X	X	X	X	X	X

Flow Cytometry ^m	X													
Serum: Total IL-18, free IL-18, IL-18BP (sample taken prior to treatment)	X	X	X	X	X	X	X	X	X	X	X	X	X	X
Anti-Tadekinig alfa antibodies (sample taken prior to treatment)		X		X		X		X	X		X	X		X
PK study measurements ^e		X ^e				X ^e								

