- h W18/Visit 8 will serve as the End of the SAOL period visit for those patients who discontinued treatment during the SAOL phase (an early termination form should be completed for these patients). These patients will not continue into the RW phase of the study.
- i Treatment of study drug administered to patients at W18/Visit 8 would be determined by randomization into RW phase. Final dose of treatment under the SAOL phase of the study will occur 2 days prior to W18/Visit 8. All W18 assessments must be performed prior to administration of study drug at W18/Visit 8.
- K Height collected at screening
- l Collection of Baseline lab samples may occur up to 3 days prior to the scheduled Week 0/Day 0 and Week 18/ Day 126 visit in order to have results available to confirm patient eligibility prior to study treatment.
- m Flow cytometry studies are necessary when a XIAP genetic abnormality has been found in the genetic testing. It is not required for patients with NLRC4 genetic mutations.

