7.5 Safety Evaluation

Safety analysis for data collected during the RW phase will be based on the RW-FAS, to include all patients who receive at least one dose of double-blind study drug during the RW phase. Patients who do not complete the study, for whatever reason, will have all available data up until the time of termination included in the analysis. For safety analysis presented by study visit, the RW Baseline value will be defined as the last value reported prior to the first dose of study drug during the RW phase.

All safety summaries for data collected during the SAOL phase will be based on the SAOL-FAS, to include all patients who receive at least one dose of TA during the SAOL phase. For safety analysis presented by study visit, the SAOL Baseline value will be defined as the last value reported prior to the first dose of TA during the SAOL phase.

7.5.1 *Extent of Exposure*

Extent of exposure to study treatment during the RW phase will be summarized for the RW-FAS by treatment group and during the SAOL phase for the SAOL-FAS for all patients combined. The duration of exposure will be presented in days and calculated as the date of last dose of study drug minus the date of first dose of study drug, plus one. The date of last dose of study drug is the date reported on the End of Treatment form, for both the end of the SAOL phase and the end of treatment during the RW phase. Duration of exposure and total number of doses received will be summarized using descriptive statistics.

7.5.2 *Adverse Events*

Treatment-emergent adverse events (TEAEs) are defined as those adverse events (AEs) with onset after the first dose of study drug or existing events that worsened after the first dose during the study. Treatment-emergent AEs occurring during the RW phase will be summarized by treatment group; TEAEs occurring during the SAOL phase will be summarized for all patients combined.

Treatment-emergent AEs occurring during the SAOL phase will be restricted to those events with onset on or after the start of dosing during the SAOL phase and prior to the start of dosing during the RW phase or 28 days after the last dose of study drug during

the SAOL phase, whichever occurs first. Events reported with a partial onset date (eg, month and year are reported but the day is missing) will be considered to be treatment-emergent if it cannot be confirmed that the event onset was prior to the first dose of study drug based on the available date entries.

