Treatment-emergent AEs occurring during the RW phase will be restricted to those events with onset on or after the start of dosing during the RW phase and prior to the first dose of study drug during the open-label extension study or 28 days after the last dose of study drug during the RW phase, whichever occurs first.

Verbatim terms on case report forms will be mapped to preferred terms and system organ classes using the Medical Dictionary for Regulatory Activities (MedDRA, version 20.0).

Summaries that are displayed by system organ class and preferred terms will be ordered by descending incidence of system organ class and preferred term within each system organ class. Summaries displayed by preferred term only will be ordered by descending incidence of preferred term. Terms with the same incidence will be ordered alphabetically. Summaries of the following types will be presented, separately for the SAOL phase and RW phase:

- Overall summary of number of unique TEAEs and treatment-emergent serious adverse events (SAEs) and patient incidence of TEAEs meeting various criteria
- Patient incidence of TEAEs by MedDRA system organ class and preferred term
- Patient incidence of TEAEs by severity grade, MedDRA system organ class, and preferred term
- Patient incidence of TEAEs by relationship to study drug, MedDRA system organ class, and preferred term
- Patient incidence of TEAEs with severity grade ≥ 3 and related to study drug by MedDRA system organ class and preferred term
- Patient incidence of treatment-emergent adverse events of special interest (AESI) by MedDRA system organ class and preferred term
- Patient incidence of SAEs by MedDRA system organ class and preferred term

At each level of summarization (eg, any AE, system organ class, and preferred term), patients experiencing more than one TEAE will be counted only once. In the summary of TEAEs by severity grade, patients will be counted once at the highest severity reported at each level of summarization; in the summary of TEAEs by relationship, patients will be counted once at the closest relationship to study drug.

In addition to the TEAE incidence summaries described above, TEAE incidence will be corrected for differences in study drug exposure by using person-time in the denominator

to calculate incidence rates. Each patient's person exposure years (PEY) will be calculated by the following:

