- As the date of onset of the TEAE of interest minus the date of first dose of study drug plus one, divided by 365.25, for those subjects who experience the TEAE of interest; or
- As the date of last dose of study drug plus 28 days, minus the date of first dose of study drug plus one, divided by 365.25, for those subjects who do not experience the TEAE of interest.

One PEY is the equivalent of one patient exposed to study drug for one year. Two patients who are exposed to study drug for half a year contribute one PEY. The total PEY of a treatment group is the sum of the person exposure years of each patient in that treatment group. Exposure-adjusted TEAE incidence will be summarized per 100 PEY as the number of patients with an event for whom person-time is available, divided by the total PEY for each treatment group and multiplied by 100. Exposure-adjusted TEAE incidence will be summarized separately for the SAOL phase and the RW phase.

Adverse event data will be presented in data listings by patient, treatment group, and event. Serious AEs, AEs leading to discontinuation of the study drug, and AESIs will be presented in separate data listings.

7.5.3 *Deaths, Other Serious Adverse Events, and Other Significant Adverse Events*

All deaths during the study as reported on the End of Treatment (SAOL), End of Treatment (RW), Study Completion/Study Discontinuation, and Adverse Event eCRFs will be listed by patient, to include the primary cause of death. Serious AEs, AEs leading to study drug withdrawal, interruption, or dose reduction of the study drug, and AESIs will be provided in separate patient data listings. AESIs include events that constitute an injection site reaction, including pruritus, erythema, and swelling.

7.5.4 *Clinical Laboratory Evaluation*

All descriptive summaries of laboratory results will be based on data analyzed by the central laboratory and presented in Système International (SI) units, as suggested by the Center for Biologics Evaluation and Research and the Center for Drug Evaluation and Research *Position on Use of SI Units for Lab Tests* (Oct 2013). All data will be included in by-patient data listings. Laboratory measurements identified as abnormal (ie, outside the normal range) will also be listed separately by patient, laboratory test, and unit. In addition, normal ranges provided by the central laboratory will be presented in a separate listing.

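### Event-free person-time in the exposure-adjusted TEAE rate runs past the close of the TEAE window, by 27 days on schedule for each SAOL patient who enters RW

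*SAP*

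**What the plan says.** SAP 7.5.2 (Adverse Events) limits SAOL TEAEs to onsets on or after the first SAOL dose "and prior to the start of dosing during the RW phase or 28 days after the last dose of study drug" of that phase, whichever is earlier. For RW the limit is "prior to the first dose of study drug during the open-label extension study or 28 days after the last dose of study drug" of RW, again whichever is earlier.

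The section then adds an exposure-adjusted rate per 100 person exposure years (PEY), reported separately for SAOL and RW. Its stated purpose is that "TEAE incidence will be corrected for differences in study drug exposure by using person-time in the denominator". A patient with the TEAE contributes time from first dose to onset. A patient without it contributes the "date of last dose of study drug plus 28 days, minus the date of first dose of study drug plus one", divided by 365.25. That second rule has no limit at the next phase or the extension, and no other part of the SAP adds one.

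Protocol Table 1, footnote i, fixes the changeover between phases: "Final dose of treatment under the SAOL phase of the study will occur 2 days prior to W18/Visit 8", and "Treatment of study drug administered to patients at W18/Visit 8 would be determined by randomization into RW phase".

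**The concern.** A rate per person-time needs events and time at risk to be cut at the same point. Here the events are cut at the first dose of the next phase, and the time of event-free patients is not. For a patient who goes straight from SAOL into RW, almost all of the 28 added days fall after the SAOL window has closed. A TEAE on those days is an RW event, but the days still enlarge the SAOL denominator and also enter that patient's RW denominator. For patients randomized to placebo they are placebo days inside the SAOL Tadekinig alfa (TA) rate.

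This is the planned path. All responders at V8 are randomized, and the protocol expects at least 10 of at most 15 patients to get there. In SAOL the direction is known: the TA rate comes out too low. In RW the extra days weigh more on short stays. If placebo patients leave earlier and start the extension promptly, the placebo rate is diluted more and the comparison tilts against TA.

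**Working it through.** The SAP states no PEY total to reproduce, so the check is date arithmetic.

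**Inputs**
- Person-time and window rules: SAP 7.5.2.
- Last SAOL dose 2 days before V8, first RW dose at V8: Protocol Table 1, footnote i. V8 is day 126 with first dose on day 0.
- Visit tolerance: "Flexibility in the visit scheduling is allowed (± 3 days) for V2 through V13" (Protocol Table 1).
- At most 15 enrolled and at least 10 randomized: Protocol synopsis. Five per arm: SAP 7.6.
- Gap from last RW dose to first extension dose, and extension uptake: not in the documents, so assumed and varied.

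**General formula.** Let F be the first dose, L the last dose and g the gap in days from L to the first dose of the next phase (g at most 28).
- Person-time without the event: L + 28 - F + 1.
- Days on which an onset can count (F to L + g - 1): L + g - F.
- Excess: 29 - g.

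**SAOL, on schedule.** F = 0, L = 124, g = 2.
- Person-time: 124 + 28 + 1 = 153 days. Window: days 0 to 125 = 126 days. Excess: 27 days.
- For a rare TEAE nearly all person-time is event-free, so the rate is low by 1 - 126/153 = 17.6%.
- V8 at day 123: 1 - 123/150 = 18.0%. V8 at day 129: 1 - 129/156 = 17.3%.
- Other gaps with V8 held at day 126: g = 5 gives 150 vs 126 days (24 excess); g = 21 gives 134 vs 126 (8 excess).

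**Commoner TEAEs** (constant hazard assumed; share q with the event by day 126). Mean time at risk within the window is 126q / (-ln(1 - q)), and the rule adds 27(1 - q).
- q = 0.4: 98.7 vs 98.7 + 16.2 = 114.9 days, 14.1% low.
- q = 0.8: 62.6 vs 62.6 + 5.4 = 68.0 days, 7.9% low.

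**Whole SAOL set, rare TEAE.** Assume 10 patients enter RW and 5 stop, keeping the full 28 days.
- All 5 stop at day 28 (57 days each): (1260 + 285)/(1530 + 285) = 1545/1815, 14.9% low.
- All 5 stop at day 124 (153 days each): (1260 + 765)/(1530 + 765) = 2025/2295, 11.8% low.

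**Example.** Ten patients enter RW; one has the event and contributes 63 days.
- As written: 9 × 153 + 63 = 1440 days, 25.4 per 100 PEY.
- Matching limits: 9 × 126 + 63 = 1197 days, 30.5 per 100 PEY.
- Difference: 1 - 1197/1440 = 16.9%.

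**Days in both phases' denominators.** Up to 10 × 27 = 270 days (0.74 PEY), of which up to 5 × 27 = 135 (0.37 PEY) are placebo days.

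**RW, patients entering the extension after a gap of k days, rare TEAE.** Person-time is L + 29 and the window L + k. L is taken as 2 days before the exit visit.

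| Patient | k = 2 | k = 14 | k = 28 |
|---|---|---|---|
| 16-week completer (L = 110) | 112/139, 19.4% low | 124/139, 10.8% | 138/139, 0.7% |
| 8-week completer or exit at V11 (L = 54) | 56/83, 32.5% low | 68/83, 18.1% | 82/83, 1.2% |

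**Apparent TA:placebo ratio when true rates are equal.** Assume exponential reactivation, hazard ratio 0.1 (SAP 7.6), exit at RW day 14, 28, 56, 84 or 112, and everyone entering the extension. Mean exit days for placebo and TA are 54.1 and 102.6 with 90% placebo reactivation, and 92.6 and 109.8 with 40% (illustrative, since SAP 7.6 reports fewer events than expected).
- k = 2, 90%: (81.1/54.1)/(129.6/102.6) = 1.19. At 40%: 1.04.
- k = 14: 1.085 and 1.02.
- k = 28: 1.005 and 1.001.

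**The case against.** The mismatch in the text is not in dispute; its reach and weight are.

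- **27 days is a scheduled value.** The excess is 29 minus the gap, and the protocol allows temporary interruptions and only advises against one between phases. This stands: an individual patient can have fewer excess days. Footnote i nevertheless plans the 2-day gap for everyone.
- **The RW figures rest on assumptions.** Extension timing and uptake are not documented, and the effect runs from 32.5% to almost nothing. The ratio model also puts every patient on the 16-week, leave-at-reactivation design, whereas SAP 6.1.5 and 7.4.2.3 show that some pooled patients had an 8-week RW phase under other rules. This stands: the RW figures show what could happen and establish no size of bias.
- **One day remains for patients with no next phase.** Read strictly, a window closing before day 28 after last dose gives 152 days against 153 of person-time. That is a matter of wording and is negligible.
- **The placement of plus one is ambiguous.** Attached to the first-dose date it would give 25 excess days. The inclusive durations in SAP 7.1.5 and 7.5.1 support 27.
- **Precision is poor.** In the example, one event in 3.94 PEY has an exact Poisson 95% interval of about 0.6 to 141 per 100 PEY, so a 17% shift would not change a clinical reading. This is fair and limits the importance. It does not excuse a systematic error of known direction that costs one sentence to remove.

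**Conclusion.** The concern holds. Followed as written, SAP 7.5.2 gives a SAOL exposure-adjusted TEAE rate that is too low and counts the same days in both phases' denominators. Per event-free patient who enters RW on schedule, the rule counts 153 days against a 126-day window. The rate among such patients is understated by up to 17.6% for a rare TEAE and by less as the TEAE becomes commoner (about 14% at 40% incidence and 8% at 80%, under constant hazard). Over the whole SAOL set it is about 12 to 15% for a rare TEAE if 10 of 15 enter RW.

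In RW the fault exists for patients who start the extension within 28 days of last dose. Its size, and any tilt between arms, depends on timing that the documents do not give. Patients who never enter the next phase or the extension are unaffected, to within one day.

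The rate is supplementary and descriptive. Crude TEAE incidence, listings, alpha and all efficacy conclusions are untouched. The point should be corrected, but it does not threaten the trial's conclusions.

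**What to change.** In SAP 7.5.2, for patients without the TEAE of interest, end person-time at the earlier of (a) last dose in the phase plus 28 days and (b) the day before the first dose of the next phase or of the open-label extension. State that first and last dose are those of the phase being summarized. Leave the TEAE window and the onset-date rule for patients with the event as they are. Stating whether day 28 itself is inside the window would also settle the remaining one-day ambiguity.

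On schedule, an event-free SAOL patient who enters RW would then contribute 126 days (0.345 PEY) instead of 153 (0.419 PEY).

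The cost is one sentence and a small program change. The RW and extension first-dose dates are already needed to assign TEAEs to phases, so no new data are collected, and the crude tables and listings do not change.

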*** NOTE:**

Laboratory safety and efficacy endpoints will be studied at the visits by the central lab. For hospitalized patients, local labs will perform, in addition, analyses as required by the standard of care and this information will be entered in the study eCRF.

PRIMARY ENDPOINTS: EFFICACY

- The primary outcome is the time to first occurrence of disease reactivation (including full and partial disease reactivation) during the 16-week RW phase.

SECONDARY ENDPOINTS

Key Secondary Efficacy Endpoint

- Response to therapy (including complete response and partial response) in the SAOL phase from Week 10 onwards and observed at least at 2 consecutive visits at least 2 weeks apart during the SAOL phase

Other Secondary Efficacy Endpoints

- Best response to therapy during the SAOL phase (including complete response and partial response and disease improvement)
- Duration of response to therapy (including complete response and partial response) during the SAOL phase
- Disease reactivation rate for individual subjects (number of disease reactivations experienced per week while each subject is on the study treatment during the SAOL phase).
- Treatment failures (i.e. patients who experience at least one disease reactivation)
- Intensity of disease reactivations (defined by the level of activity given by the mAIDAI – both objective and subjective criteria)
- Serum CRP
- Serum Ferritin
- Improvement of fevers (if present at Baseline)
- Improvement of hepato/splenomegaly (if present at Baseline)
- Improvement in serum albumin and liver transaminases, anemia and/or platelet count (if present at Baseline)

- Hospital length of stay
- Physician Global Assessment
- Patient's/Caregiver's qualitative evaluation of health status
- Presence of skin rash (evolution if present at Baseline or appearance during the study)
- Tolerance to oral/enteral nutrition for hospitalized patients if intestinal dysfunction was present at Baseline
- Improvement of stool output for hospitalized patients if intestinal dysfunction was present at Baseline

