audio) to enable site staff to conduct “virtual” (not in-person) visits with their patients. These visits may be supported by home health nurses assisting in physical examination or performance of blood draws. Laboratory assessments may be also performed at qualified local laboratories. The study site may also utilize a physical examination from the patient’s most recent standard of care visit conducted by the local treating physician, for the purpose of the study.

Patients and/or parents (or legal representative, if applicable) will sign a respective assent/informed consent prior to the conduct of such telemedicine visits.

Further details about the different possibilities for the conduct of telemedicine visits are described in section 14.1.

STATISTICAL ANALYSIS

Statistical analysis:

Data will be analyzed on an intent-to-treat basis. Baseline patient and disease characteristics according to treatment arm will be presented using standard descriptive statistics.

Comparative statistical analyses will be performed on data collected during the RW phase. The primary endpoint is time to first occurrence of disease reactivation (including full and partial disease reactivation) during the RW phase. Tadekinig alfa will be compared to placebo using the log rank test at the alpha = 0.05 level of significance (2-sided). Kaplan-Meier estimates of the distribution of time-to-event will be summarized and graphed by treatment group.

To test the efficacy of Tadekinig alfa on secondary outcomes during the RW, Fisher's exact test will be utilized for binary outcomes (i.e. treatment failure rate) and a non-parametric, Mann-Whitney-Wilcoxon test will be utilized for continuous outcomes (i.e. change in the mAIDAI). To assess the impact of possible variation in baseline measures, an analysis of covariance (ANCOVA) model with covariate adjustment for Baseline may be considered as a sensitivity analysis, or alternative non-parametric approaches if normality assumptions are not met.

If the primary analysis is statistically significant ($p < 0.05$), the following secondary endpoints measured during the RW phase will be analyzed using a fixed-sequence testing procedure in the order specified below to control the overall level of significance:

- Treatment failure rate;
- Change from RW baseline to Week 34 (i.e. Week 16 of the RW phase) or End of Study Visit in the mAIDAI total score; and

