Clinical laboratory measurements including serum chemistry, hematology, coagulation, and erythrocyte sedimentation rate will be summarized separately for the SAOL phase and the RW phase by treatment group. Descriptive statistics will be presented for

observed values and changes from each respective baseline at each visit where parameters were scheduled to be collected per the clinical study protocol.

Where applicable, laboratory results will be classified as “low,” “normal,” or “high” with respect to the parameter-specific reference ranges (ie, below the lower limit of the normal range, within the normal range, or above the upper limit of the normal range). Three-by-three contingency tables will be presented for each study phase and laboratory parameter to summarize the shift from the baseline category to the worst post-baseline measurement, defined as the value numerically farthest outside of the normal range across all post-baseline visits through the end of the study. Summary results will include the count and percentage of patients within each shift category and treatment group. Percentages will be based on the number of patients with a non-missing baseline value and at least one non-missing post-baseline value.

Where applicable, hematology, chemistry, and coagulation results for selected parameters will be assigned a toxicity grade based on the U.S. Department of Health and Human Services *Common Terminology Criteria for Adverse Events (CTCAE)*, version 5.0 (27 Nov 2017). If the quantitative criteria for grading are equivalent for two grades and the differentiation is described by clinical interventions, the clinical intervention component will not be considered and the highest CTCAE grade will be assigned. Similarly, death related to AE (ie, Grade 5) cannot be determined with available laboratory-based data collection and, thus, will not be summarized as a category. Laboratory parameters that include multiple sets of criteria for each direction (eg, separate criteria for potassium measures to assess hyperkalemia and hypokalemia) will be summarized separately to reflect each set of criteria.

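### SAP 7.5.4 allows only central-laboratory data into its summaries yet promises tables of ESR, which is run locally; its by-phase shift tables take the worst value through the end of the study, so the SAOL table can include RW values.

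*SAP*

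**What the plan says.** **Source of laboratory data.** SAP 7.5.4 opens with the rule that "All descriptive summaries of laboratory results will be based on data analyzed by the central laboratory". It adds that "All data will be included in by-patient data listings", and it lists out-of-range values separately. It makes no exception for any analyte.

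**ESR.** The next paragraph of SAP 7.5.4 says: "Clinical laboratory measurements including serum chemistry, hematology, coagulation, and erythrocyte sedimentation rate will be summarized separately for the SAOL phase and the RW phase". ESR is also a listed safety variable in SAP 6.4.2 and Protocol 8.5.1. In Protocol Table 1 (Section 7), the laboratory row that covers every laboratory visit carries the label "ESR (at local lab".

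**Worst value.** SAP 7.5.4 plans a three-by-three shift table for each phase and parameter, from the baseline category to the worst post-baseline measurement. It defines the worst as the value farthest outside the normal range "across all post-baseline visits through the end of the study". The five-by-five toxicity-grade tables are also by phase, but they give no window for the worst grade.

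**The concern.** Each rule conflicts with another statement in the plan, and a programmer following the text cannot satisfy both.

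For ESR, the choice would be between an empty table and an unplanned departure from the SAP.

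For the shift tables, a table headed SAOL would mix open-label values with values from the blinded phase, including those of patients withdrawn to placebo. The same RW value could then count in both phase tables. Adverse-event tables for the same phase would cover a different period, because SAP 7.5.2 ends SAOL events no later than the start of RW dosing.

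With at most 15 patients enrolled, one reclassified patient moves a percentage by at least 1/15, or 6.7 points.

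**Working it through.** The plan gives no figure to reproduce here, so the check compares the texts and counts visits.

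**1. ESR.**
- Central-only rule: SAP 7.5.4, without exception.
- Where ESR is run: Protocol Table 1 says local for all laboratory visits.
- Visit lists in Protocol 14.2 to 14.9: the local laboratory is named for ESR at screening, V1 to V5 and V13 (7 of the 14 visits V0 to V13). No laboratory is named at V6 to V12 (the other 7).
- The only local fallback found in the SAP is in 7.1.4, for CRP reported as below 3 mg/L.

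Under Table 1, no ESR result qualifies. Suppose instead that the seven unlabelled visits were read as central. Both visits before the first SAOL dose (screening and V1) are still labelled local. There would be no eligible SAOL baseline, so no SAOL change or shift in ESR could be computed.

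**2. Worst-value window for a randomized patient (Protocol Table 1).**
- SAOL post-baseline visits: V2 to V8 = 7.
- RW visits: V9 to V13 = 5.
- Window to the end of the study: 7 + 5 = 12. Share from the RW phase: 5/12 = 42%.
- In days: V8 is Day 126 and V13 is Day 238, so (238 − 126)/238 = 112/238 = 47%.

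Twelve is the maximum. A patient who reactivates goes early to the End of Study visit and contributes fewer RW visits. Under the 8-week RW phase, whose last visit SAP 7.7 gives as Week 26 (V11), at most V9 to V11 are added: 3 of 10 visits, or 30%. A patient who is not randomized is unaffected.

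**3. Direction.** The worst of a larger set of values is never closer to the normal range than the worst of a subset. The longer window can therefore only leave a patient's SAOL result unchanged or move it further out of range.

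**4. Illustration.** Assume independent visits, each with chance *p* of an out-of-range value. The documents give no *p*, so a range is shown. The chance of at least one such value in *n* visits is 1 − (1 − *p*)^*n*.

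| *p* | *n* = 7 | *n* = 12 |
|---|---|---|
| 0.02 | 13% | 22% |
| 0.05 | 30% | 46% |
| 0.10 | 52% | 72% |
| 0.20 | 79% | 93% |

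Visits within a patient are in truth correlated, which would narrow these gaps.

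**5. The RW table.** The end of the study is the end of the RW phase, so its window is V9 to V13 under either wording.

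**The case against.** **Intent is clear from context.** SAP 7.5 describes its summaries by the phase in which data were collected. SAP 6.4.2 pairs SAOL baseline with SAOL data and RW baseline with RW data. SAP 7.1.3 says that all visits count when a worst value is derived, so the disputed phrase may have been meant only to bring in unscheduled and early-termination visits. Likewise, an explicit promise to tabulate ESR shows that ESR was meant to be tabulated. This is a fair account of intent, but it does not override an explicit definition. The phase-specific rule in SAP 7.1.2 covers changes from baseline and reactivations, and does not mention worst values. For ESR, the protocol's general note (Section 13) that visit laboratory endpoints are studied centrally is weaker than a schedule row that names the local laboratory.

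**A stronger reading does not hold.** A reader might infer that the central-only rule discards local results and so understates laboratory safety, above all in hospital. The documents do not support that:
- Local results stay in the by-patient listings. Clinically significant abnormalities that meet the AE definition are recorded as AEs whatever the laboratory (Protocol 17.6).
- Hospital tests come on top of the visit samples: "For hospitalized patients, local labs will perform, in addition, analyses as required by the standard of care".
- For telemedicine, "Laboratory assessments may be also performed at qualified local laboratories" is an option, not the rule. Protocol 14.1 also has home nurses draw central-laboratory samples.

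Some local-only results can still arise, because Protocol 14.10 avoids duplicate central and local tests where possible. Their number is not given.

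**Pooling has its own cost.** If every hospital result entered the worst-value tables, the worst value would depend on how often a patient was sampled. An arm with more hospital stays could look worse for that reason alone. This objection stands, and such pooling is not asked for.

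**Conclusion.** Two statements in SAP 7.5.4 fail as written. The ESR tables have no eligible data if ESR is run locally as scheduled. The SAOL three-by-three shift table searches up to 12 scheduled visits instead of 7, and the added visits are blinded RW visits, some on placebo.

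The second conclusion rests on the literal definition. The rest of the SAP suggests that a phase-limited window was meant, which is a reason to correct the wording and not to leave it. It would be too much to say that every phase table is distorted: the RW table is not, and the five-by-five tables lack a window without containing the end-of-study phrase.

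The effect is confined to descriptive safety tables. The primary test, its alpha and its power are untouched. SAP 7.5.4 does not say whether its central-only sentence reaches the CRP and ferritin efficacy summaries in 7.4.4.3, so no conclusion is drawn there. This should be corrected before database lock and unblinding, but it does not threaten the trial's main conclusion.

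**What to change.** In SAP 7.5.4:

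1. State that ESR is summarized from local-laboratory results, as an exception to the central-only rule.
2. End the worst-value window with the respective phase. For SAOL: after the first SAOL dose and before the first RW dose, or to the end of the SAOL phase for patients not randomized. For RW: after the first RW dose to the end of the RW phase. Apply the same windows to the five-by-five tables.
3. For a scheduled visit with only a local result, such as a telemedicine visit, a flagged local value judged against that laboratory's own range may be used, with a central-only table as a check.
4. Leave the extra hospital results in the listings.

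The cost is a few clauses and some programming. Protocol 15.1 already has outside-laboratory results entered in the eCRF. The sponsor should confirm that local reference ranges are also captured, since SAP 7.5.4 plans a listing of central ranges only. The downside of item 3 is a mixture of laboratories within a summary, which the flag and the central-only table make visible.
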